Visit Number	1	2	3	4	5	6	7, 8, 9	10+		Treatment discontinued	28 days ^c	Progression follow-up ^d
Cycles / Day	C1			C2 D1	C3 D1	C4, 5, 6 D1	C7 to 3.5 years D169- 1277	3.5 Years to Disease Progression D1278+				
	D1	D8	D15									
Day	-28 to -1	1	8	15	29	57	85, 113, 141	Every 8 weeks	Every 10 weeks			Every 8 weeks prior to Day 1277/ Every 10 weeks thereafter
Window (Days)		0	±2	±2	±2	±7	±7	±7	±14	±7	+7	± 7/± 14
Physical examination, including weight and eyes ^h	x	x		x	x	x	x	x	x	x		
Height	x											
WHO performance status	x	x		x	x	x	x	x	x	x		once at start of subsequent anticancer treatment
Vital signs	x	x	x	x	x	x	x	x	x	x		

	Screening/ Enrolment ^a	Treatment Period (further treatment cycles as per C7) ^b									Follow-up Period	
Visit Number	1	2	3	4	5	6	7, 8, 9	10+		Treatment discontinued	28 days ^c	Progression follow-up ^d
Cycles / Day		C1							C7 to 3.5 years D169- 1277	3.5 Years to Disease Progression D1278+		
Day	-28 to -1	1	8	15	29	57	85, 113, 141	Every 8 weeks	Every 10 weeks			Every 8 weeks prior to Day 1277/ Every 10 weeks thereafter
Window (Days)		0	±2	±2	±2	±7	±7	±7	±14	±7	+7	± 7/± 14
Clinical chemistry/ Haematology/ Urinalysis ^h	x	x	x	x	x	x	x	x	x	x		
ECG ⁱ	x	x	x	x	x	x	x	x	x	x		
Echocardiogram/ MUGA (for LVEF) ^j	(x)		At least every 16 weeks up to 3.5 years on study drug and then at least every 20 weeks for as long as on study drug							If clinically indicated		
Tumour assessments (RECIST) ^k	x					x	C5D1 and every 8 weeks until Day 1277		Every 10 weeks until progression			x

	Screening/ Enrolment ^a	Treatment Period (further treatment cycles as per C7) ^b									Follow-up Period	
Visit Number	1	2	3	4	5	6	7, 8, 9	10+		Treatment discontinued	28 days ^c	Progression follow-up ^d
Cycles / Day		C1			C2 D1	C3 D1	C4, 5, 6 D1	C7 to 3.5 years D169- 1277	3.5 Years to Disease Progression D1278+			
		D1	D8	D15								
Day	-28 to -1	1	8	15	29	57	85, 113, 141	Every 8 weeks	Every 10 weeks			Every 8 weeks prior to Day 1277/ Every 10 weeks thereafter
Window (Days)		0	±2	±2	±2	±7	±7	±7	±14	±7	+7	± 7/± 14
Dispense study medication		X			X	X	X	X	X			
Dose with osimertinib					Daily dosing							
Concomitant medication and procedures		X	X	X	X	X	X	X	X	X	X	(once) ¹
AEs		X	X	X	X	X	X	X	X	X	X	(once) ¹
First subsequent anticancer treatment ^m											X	X

- ^a Consent must be taken prior to 28-day screening period. Screening period will start with first study-related assessment.

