2.2 Protocol deviations

The following general categories will be considered important protocol deviations which will be listed and discussed in the clinical study report (CSR) as appropriate for the study:

- Informed consent procedure deviation (eg, no informed consent signed prior to any screening procedure)
- Eligibility criteria deviation (eg, any inclusion criteria not met or exclusion criteria met)
- Received prohibited concomitant medications (or unable to stop use prior to receiving the first dose of study drug) or herbal supplements known to be potent inducers of cytochrome P450 (CYP) 3A4 (at least 3 weeks prior). Please refer to protocol Section 3.5 for those medications that are detailed as ‘not to be administered’ or being ‘restricted concomitant medications’. These will be used as a guiding principle for the physician review of all medications prior to database lock.
- Management of adverse events: Lack of prompt reporting of cases meeting Hy’s law criteria and serious adverse events (SAE) not being reported within 24 hours of awareness of the event.
- Tumour biopsy sample taken from lesion selected for RECIST assessment (unless only one lesion exists and the RECIST scans are performed within 14 days of screening biopsy).
- No baseline RECIST 1.1 assessment before start of treatment.
- RECIST 1.1 assessments not done every 8 weeks (± 7 days) in relationship to the date of first dose until RECIST 1.1 defined progression.
- Screening assessment not performed within 42 days prior to study drug initiation.

If the number of deviations which are considered to have the potential to impact the primary analysis is considered important, sensitivity analyses may be performed on subgroups. This will be decided during the data review meeting and before the database lock. The final classification of protocol deviations will be made prior to database lock. Any other deviations from monitoring notes or reports will be reported in an appendix to the CSR.

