3. PRIMARY AND SECONDARY VARIABLES

3.1 Efficacy

3.1.1 Derivation of RECIST visit responses

For all patients, the RECIST tumour response data will be used to determine each patient’s visit response according to RECIST version 1.1. It will also be used to determine if, and when, a patient has progressed in accordance with RECIST and their best objective response to study drug.

Baseline radiological tumour assessments are to be performed no more than 28 days before the first dose of treatment, and as close as possible to the start of study treatment. Assessments on the day of the first dose where neither time nor a nominal pre-dose indicator are captured will be considered prior to the first dose if such procedures are required by the protocol to be conducted before the first dose. Tumour assessments are then performed every 8 weeks (± 1 week) following the start of study treatment until objective disease progression.

If an unscheduled assessment is performed, and the patient has not progressed, every attempt should be made to perform the subsequent assessments at their scheduled visits. This schedule is to be followed to minimise any unintentional bias caused by some patients being assessed at a different frequency than other patients.

From the Investigator's review of the imaging scans, the RECIST tumour response data will be used to determine each patient's visit response according to RECIST 1.1. At each visit, patients will be programmatically assigned a RECIST 1.1 visit response of complete response (CR), partial response (PR), stable disease (SD) or progressive disease (PD), using the information from target lesions (TLs), non-target lesions (NTLs) and new lesions and depending on the status of their disease compared with baseline and previous assessments. If a patient has had a tumour assessment that cannot be evaluated then the patient will be assigned a visit response of not evaluable (NE), (unless there is evidence of progression in which case the response will be assigned as PD).

Please refer to [Table 4](#) for the definitions of CR, PR, SD, and PD.

RECIST outcomes (ie, PFS, ORR etc.) will be calculated programmatically for the site Investigator data (see [Section 3.2](#)) from the overall visit responses.

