3.2.2.1 Progression-free survival

PFS is defined as the time from the first dose of osimertinib until the date of RECIST 1.1-defined progression or death (by any cause in the absence of progression) regardless of whether the patient withdraws from therapy or receives another anticancer therapy prior to progression. PFS is calculated in months as follows:

$$PFS = \frac{\text{date of objective disease progression or censoring} - \text{date of first dose of osimertinib} + 1}{30.4375}$$

Patients who have not progressed or died at the date of analysis will be censored at the time of the latest date of assessment from their last evaluable RECIST 1.1 assessment.

However, if the patient progresses or dies after two or more missed visits (126 days), the patient will be censored at the time of the latest evaluable RECIST 1.1 assessment.

Given the scheduled visit assessment scheme (i.e., eight-weekly for the first 3.5 years [D1277] then ten-weekly thereafter) the definition of 2 missed visits will change. Due to a delay in enacting CSP version 5.0 there was some variability in when patients transitioned to 10-weekly visit. However, we will apply the following rules to all patients.

1. If the previous RECIST 1.1 assessment is baseline, then two missing visits will equate to 17 weeks since the previous RECIST 1.1 assessment, allowing for a late visit (i.e., 2×8 weeks + 1 week for a late assessment = 17 weeks [119 days]).
2. If the previous RECIST 1.1 assessment is post baseline and \leq study day 1169, then two missing visits will equate to 18 weeks since the previous RECIST 1.1 assessment, allowing for early and late visits (i.e., 2×8 weeks + 1 week for an early assessment + 1 week for a late assessment = 18 weeks [126 days]).
3. If the previous RECIST 1.1 assessment study day is > 1169 and ≤ 1225 , then the two missed visits occur over the period when the scheduled frequency of RECIST 1.1 assessments changes from eight-weekly to ten-weekly, then this will equate to 21 weeks (i.e., take the average of 8 and 10 weeks which gives 9 weeks and then apply same rationale, hence 2×9 weeks + 1 week for an early assessment + 2 week for a late assessment = 21 weeks [147 days]).
4. If the previous RECIST 1.1 assessment study day is > 1225 (when the scheduling changes to ten-weekly assessments), two missing visits will equate to 24 weeks (i.e., 2×10 weeks + 2 week for an early assessment + 2 week for a late assessment = 24 weeks [168 days]).

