If the patient has no evaluable post-baseline visits or does not have baseline data, they will be censored at Day 1 unless they die within two visits of baseline (16 weeks plus 1 week allowing for a late assessment within the visit window).

The PFS time will always be derived based on scan/assessment dates not visit dates.

RECIST 1.1 assessments/scans contributing towards a particular visit may be performed on different dates. The following rules will be applied:

- Date of progression will be determined based on the earliest of the dates of the component that triggered the progression.
- When censoring a patient for PFS, the patient will be censored at the latest of the RECIST assessment/scan dates contributing to a particular overall visit assessment.

Overall visit assessments will be determined for each assessment (scheduled or unscheduled) and will contribute to the derivation of PFS.

Objective progression is defined as at least a 20% increase in the sum of the diameters of the target lesions (compared to previous minimum sum) and an absolute increase of >5 mm, or an overall non-target lesion assessment of progression or a new lesion.

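### PFS rule 1 counts its 119-day limit from the baseline scan, so an on-time Week 16 progression can be censored after only one missed scan

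*SAP*

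**What the plan says.** SAP 3.2.2.1 censors a progression or death that follows two or more missed visits and gives four rules for what that means. Rule 1 reads: "If the previous RECIST 1.1 assessment is baseline, then two missing visits will equate to 17 weeks since the previous RECIST 1.1 assessment". Its derivation is 2 × 8 weeks plus one week for lateness, 119 days. Beyond the limit, "the patient will be censored at the time of the latest evaluable RECIST 1.1 assessment". A separate sentence covers patients without evaluable post-baseline visits or without baseline data: "they will be censored at Day 1 unless they die within two visits of baseline", given as 16 weeks plus 1.

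On scan timing, SAP 3.1.1 says "Baseline radiological tumour assessments are to be performed no more than 28 days before the first dose of treatment". It asks for this scan to be near the start of dosing, and schedules later scans every 8 weeks, plus or minus 1 week, "following the start of study treatment until objective disease progression". SAP 2.2 judges scan deviations "in relationship to the date of first dose until RECIST 1.1 defined progression". SAP Table 1 has a scan at C3D1 (Day 57), then "C5D1 and every 8 weeks until Day 1277"; C5D1 is Day 113.

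Other places use a different anchor. Protocol 5.1.1 and SAP Table 1 footnote k run the schedule from study enrolment. SAP 4.2.1 equates being enrolled with having consented, and Protocol Table 2 footnote a puts consent before the screening period. Protocol 3.7.1, however, uses enrolled for a step taken after screening is passed.

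**The concern.** The 119 days has room for two 8-week intervals and one late week, but none for the gap between baseline scan and first dose. If scans are scheduled from first dose, that gap is added to the time from baseline to every later scan. A patient who missed only the Week 8 scan can then exceed the limit at an in-window Week 16 scan, and the progression found there is discarded. Protocol 8.4.2 censors only after two or more missed visits, and SAP section 6 declares no departure from it.

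The censoring date is also unclear. Read literally, it is the pre-dose scan, which gives a negative PFS time. The Day 1 rule does not clearly apply, because the progression scan is itself a post-baseline visit. The death exception names baseline as its start without saying whether that means the scan date or Day 1.

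PFS is the first-listed secondary endpoint. The error can only remove early events, so any bias is upward and falls mainly on the 6-month rate planned in SAP 4.2.9.2.

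**Working it through.** **Reproducing the plan's limits.** Rule 1: (2 × 8 + 1) × 7 = 119 days. Rule 2: (2 × 8 + 2) × 7 = 126. Rule 3: (2 × 9 + 3) × 7 = 147. Rule 4: (2 × 10 + 4) × 7 = 168. All four match the SAP. Rule 1 has the tightest limit although baseline has the widest window. Counted from the baseline scan with rule 2's logic, it would be 28 + 112 + 7 = 147.

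**First-dose anchor.** Inputs: baseline scan x days before Day 1 (x up to 28, SAP 3.1.1); Week 16 target Day 113, window Days 106 to 120 (SAP Table 1); no Study Day 0 (SAP 4.1). The gap from baseline to a scan on study day D is (D − 1) + x. The limit is taken as exceeded when the gap is more than 119 days.

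| Week 16 scan | Gap (days) | Censored when |
|---|---|---|
| Day 106 (early) | 105 + x | x ≥ 15 |
| Day 113 (on time) | 112 + x | x ≥ 8 |
| Day 120 (late, in window) | 119 + x | x ≥ 1 |

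For the on-time scan, x = 7 gives 119 (kept) and x = 8 gives 120 (censored), so 21 of the 28 possible baseline days lead to censoring. Counting 119 itself as over the limit, or counting days inclusively, lowers the threshold to 7.

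**Enrolment anchor.** Let enrolment be e days before Day 1. The on-time Week 16 gap is 112 − e + x.
- If enrolment is consent, then e ≥ x. The gap is at most 112 on time and 119 if a week late, so nothing is wrongly censored.
- If enrolment follows screening, the problem arises when x − e is 8 or more.

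**One affected patient, Day −28 scan.** Literal censoring date: (−28 + 1)/30.4375 = −0.89 months. Day 1 rule: 1/30.4375 = 0.03 months. The correct result is an event at 113/30.4375 = 3.71 months.

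**Number affected.** The 19-month exponential median is the plan's own (Protocol 8.1). P(event by Day 113) = 1 − exp(−(ln 2/19) × 3.71) = 12.7%. The documents give no missed-scan rate and no distribution of baseline timing. I assume 2–15% miss Week 8 and 50–100% have x ≥ 8.
- Low: 150 × 0.02 × 0.5 × 0.127 = 0.19
- High: 150 × 0.15 × 1.0 × 0.127 = 2.9

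**Effect on PFS.** Censoring k early events near time 0 gives S′(t) = S(t) × 150/(150 − k), and a median shift of 19 × log2(150/(150 − k)).

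| k | 6-month PFS (80.3% without the error) | Median shift (months) |
|---|---|---|
| 0.19 | 80.4% | 0.03 |
| 1 | 80.9% | 0.18 |
| 3 | 82.0% | 0.55 |

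The sampling SD of the median without censoring is (19/ln 2)/√150 = 2.24 months. A simulation of 3,000 trials (n = 150, follow-up uniform from 26 to 38 months) gave mean shifts of 0.17 and 0.54 for k = 1 and 3, and an SD of 2.26.

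**The case against.** The strongest reply is that the protocol's schedule runs from enrolment, as does SAP Table 1 footnote k, and that SAP 4.2.1 treats enrolment as consent. On that reading 119 days fits and no in-window Week 16 scan is lost. This stands as a condition on the finding. It does not remove it, because the SAP's own derivation section, its deviation list and its visit days all use first dose.

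The upper figure is also soft, for these reasons:
- It needs every baseline scan to be 8 or more days pre-dose, against the instruction to scan close to treatment start.
- Its 12.7% includes deaths, and a death within 119 days of the baseline scan is kept.
- A Week 8 scan rated not evaluable may fall under rule 2, and unscheduled scans may catch progression earlier.
- The first-line phase I cohorts in Protocol 1.1 had 72% progression-free at 12 months. A constant hazard through that point gives 1 − 0.72^(3.71/12) = 9.7% by Day 113 and a ceiling of 150 × 0.15 × 0.097 = 2.2.

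All of this is fair, so 2.9 should be read as a ceiling.

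The lead sentence of SAP 3.2.2.1 gives 126 days, not 119. The four rules are said to apply to all patients, so 119 governs. Even 126 days from the scan would censor an on-time Week 16 progression once x reaches 15.

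Finally, PFS is a secondary endpoint in a single-arm exploratory study. That limits the consequence but does not justify leaving the rule as written.

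**Conclusion.** The concern holds. Under the first-dose schedule in SAP 3.1.1 and 2.2, rule 1 censors an on-time Week 16 progression after one missed scan whenever the baseline scan was 8 or more days before Day 1, contrary to Protocol 8.4.2. Under enrolment-as-consent it does not. The documents support both anchors, and that inconsistency needs correcting in its own right.

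The likely size is a fraction of a patient up to about 3 of 150, resting on assumed missed-scan and baseline-timing rates. The resulting upward shift in PFS is well inside sampling error, and the primary endpoint is not touched. It is worth correcting because the bias has one direction and the rule departs from the protocol, not because it would change the trial's conclusions.

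**What to change.** In SAP 3.2.2.1, when the last assessment is baseline:

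1. Count the 119 days from first dose, so that events through Day 120 count.
2. Use the same clock for the death exception.
3. State Day 1 as the censoring date.
4. Bring the 126 days in the lead sentence into line with the four rules.

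State one scan anchor and one meaning of enrolment across the protocol and SAP.

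Under the first-dose anchor, the latest in-window Week 16 scan is 119 days after Day 1 and is kept. The earliest in-window Week 24 scan, after two missed scans, is at 161 days and is censored. Under the enrolment anchor these become 119 − e and 161 − e. At e = 28 the second is 133, and it stays above 119 for e up to 41. Consent has no stated upper limit before screening, so a longer interval would need the anchor settled first.

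Keeping the scan clock and adding 28 days (147) also separates the two cases under the first-dose anchor: at most 147 days with one missed scan, at least 162 with two. It is less robust under the enrolment anchor, where e = 28 and x = 1 put the early Week 24 scan at 161 − 28 + 1 = 134 days.

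A separate wording point: SAP 3.2.2.1 requires an absolute increase above 5 mm, whereas SAP Table 4 and Protocol Table F2 accept exactly 5 mm. Align it to at least 5 mm. No PFS effect is claimed, because SAP 3.1.1 derives PFS from the Table 4 visit responses.

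The cost is a few wording edits and a small programming change before database lock, with no new data.

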Baseline assessments should encompass all areas of known predilection for metastases in the disease under evaluation and should additionally investigate areas that may be involved based on signs and symptoms of individual patients and should be performed no more than 28 days before the start of study treatment (refer to Study Plan and Section 5.1 from the study protocol). Follow-up assessments will be performed every 8 weeks (\pm 7 days) (relative to study enrolment) up to 3.5 years (1277 days) and every 10 weeks (\pm 14 days) from Day 1278 to progression as defined by RECIST 1.1 even if a patient discontinues treatment prior to progression or receives other anticancer treatment. Any other sites at which new disease is suspected should also be adequately imaged at follow-up.

If an unscheduled assessment was performed and the patient has not progressed, every attempt should be made to perform the subsequent assessments at their scheduled visits. This schedule is to be followed in order to minimise any unintentional bias caused by some patients being assessed at a different frequency than other patients.

F 4.2 Target Lesions

F 4.2.1 Documentation of Target Lesions

A maximum of 5 measurable lesions, with a maximum of 2 lesions per organ (including lymph nodes), representative of all lesions involved should be identified as TL at baseline. Target lesions should be selected on the basis of their size (longest diameter for non-nodal lesions or short axis for nodal lesions), but in addition should be those that lend themselves to reproducible repeated measurements. It may be the case that, on occasion, the largest lesion does not lend itself to reproducible measurement in which circumstance the next largest lesion, which can be measured reproducibly, should be selected.

The site and location of each TL should be documented as well as the longest diameter for non-nodal lesions (or short axis for lymph nodes). All measurements should be recorded in millimetres. At baseline the sum of the diameters for all TL will be calculated and reported as the baseline sum of diameters. At follow-up visits the sum of diameters for all TL will be calculated and reported as the follow-up sum of diameters.

Special cases:

- For TL measurable in 2 or 3 dimensions, always report the longest diameter. For pathological lymph nodes measurable in 2 or 3 dimensions, always report the short axis.

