- If the CT/MRI slice thickness used is $> 5\text{mm}$, the minimum size of measurable disease at baseline should be twice the slice thickness of the baseline scan.
- If a lesion has completely disappeared, the longest diameter should be recorded as 0 mm.

- If a TL splits into 2 or more parts, then record the sum of the diameters of those parts.
- If 2 or more TL merge then the sum of the diameters of the combined lesion should be recorded for one of the lesions and 0 mm recorded for the other lesion(s).
- If a TL is believed to be present and is faintly seen but too small to measure, a default value of 5 mm should be assigned. If an accurate measure can be given, this should be recorded, even if it is below 5 mm.
- If a TL cannot be measured accurately due to it being too large, provide an estimate of the size of the lesion.
- When a TL has had any intervention eg, radiotherapy, embolisation, surgery, during the study, the size of the TL should still be provided where possible.

F 4.2.2 Evaluation of Target Lesions

This section provides the definitions of the criteria used to determine objective tumour visit response for TL.

Table F2 Evaluation of Target Lesions

Complete Response (CR)	Disappearance of all target lesions since baseline. Any pathological lymph nodes selected as target lesions must have a reduction in short axis to < 10 mm
Partial Response (PR)	At least a 30% decrease in the sum of the diameters of TL, taking as reference the baseline sum of diameters
Stable Disease (SD)	Neither sufficient shrinkage to qualify for PR nor sufficient increase to qualify for progressive disease
Progressive Disease (PD)	At least a 20% increase in the sum of diameters of target lesions, taking as reference the smallest sum on study (this includes the baseline sum if that is the smallest on study). In addition to the relative increase of 20%, the sum must also demonstrate an absolute increase of at least 5mm
Not Evaluable (NE)	Only relevant if any of the target lesions were not assessed or not evaluable or had a lesion intervention at this visit. Note: If the sum of diameters meets the PD criteria, PD overrides not evaluable as a target lesion response

F 4.3 Non-target Lesions

F 4.3.1 Evaluation of Non-target Lesions

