PD	At least a 20% increase in the sum of the diameters of TLs, taking as reference the smallest sum on study (this includes the baseline sum if that is the smallest on the study). In addition to the relative increase of at least 20%, the sum must also demonstrate an absolute increase of at least 5 mm.
NE	Only relevant if any of the TLs were not assessed or not evaluable or had a lesion intervention at this visit. Note: If the sum of diameters meets the progressive disease criteria, progressive disease overrides not evaluable as a TL response.
NA	No TLs are recorded at baseline.

Abbreviations: CR = Complete response; NA = Not applicable; NE = Not evaluable; PD = Progressive disease; PR = Partial response; SD = Stable disease; TL = Target lesion.

Rounding of TL data

For calculation of PD and PR for TLs, percentage changes from baseline and previous minimum should be rounded to one decimal place before assigning a TL response. For example, 19.95% should be rounded to 20.0% but 19.94% should be rounded to 19.9%.

Missing TL data

For a visit to be evaluable, all TL measurements should be recorded. However, a visit response of PD should still be assigned if any of the following occurred:

- A new lesion is recorded.
- A NTL visit response of PD is recorded.
- The sum of TLs is sufficiently increased to result in a 20% increase, and an absolute increase of ≥ 5 mm, from nadir (defined below) even assuming the non-recorded TLs have disappeared.

The nadir (ie, the smallest measurement based on the same set of lesions at baseline and on a given visit) can only be taken from assessments where all the TLs had a longest diameter (LD) recorded.

Lymph nodes

For lymph nodes, if the size reduces to <10 mm, these are considered non-pathological.

However, a size will still be measured, and this size should still be used to determine the TL visit response as normal. In the special case where all lymph nodes are <10 mm and all other TLs are 0 mm, then although the sum may be >0 mm, the calculation of TL response should be overwritten as a CR.

TL visit responses subsequent to CR

A CR response can only be followed by CR, PD or NE. If a CR has occurred, then the following rules at the subsequent visits must be applied:

- Step 1: If all lesions meet the CR criteria (ie, 0 mm or <10 mm for lymph nodes), the response will be set to CR irrespective of whether the criteria for PD of TL is also met for lymph node (ie, if a lymph node LD increases by 20% but remains <10 mm).

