- Step 2: If some lesion measurements are missing but all other lesions meet the CR criteria (ie, 0 mm or <10 mm for lymph nodes), the response will be set to NE irrespective of whether the criteria for PD is also met when referencing the sum of TL diameters.
- Step 3: If not all lesions meet the CR criteria, and the sum of lesions meets the criteria for PD, the response will be set to PD.
- Step 4: If, after steps 1 through 3, a response can still not be determined, the response will be set to remain as CR.

TL too big to measure

If a TL becomes too big to measure, this should be indicated in the database and an estimated size ('x') above which it cannot be accurately measured should be recorded. If using a value of x in the calculation of TL response would not give an overall visit response of PD, then this will be flagged and reviewed by the study team. It is expected that a visit response of PD will remain in the vast majority of cases.

TL too small to measure

If a TL becomes too small to measure, then this will be indicated as such on the case report form and a value of 5mm will be entered into the database and used in TL calculations. However, a smaller value may be used if the radiologist has not indicated 'too small to measure' on the case report form and has entered a smaller value that can be reliably measured. If a lesion has completely disappeared, the longest diameter should be recorded as 0 mm.

Irradiated lesions/lesion intervention

Previously irradiated lesions (ie, lesion irradiated prior to entry into the study) should be recorded as NTLs and should not form part of the TL assessment.

Any TL (including lymph nodes) which has had intervention during the study (for example, irradiation/palliative surgery/embolization) should be handled in the following way and once a lesion has had intervention then it should be treated as having intervention for the remainder of the study, noting that an intervention will most likely shrink the size of tumours:

- Step 1: The diameters of the TLs (including the lesions that have had intervention) will be summed and the calculation will be performed in the usual manner. If the visit response is PD this will remain as a valid response category.

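### SAP 3.2.2.1 sets target-lesion progression at more than 5 mm, where the protocol and the rest of the SAP say at least 5 mm; the rules differ only at exactly +5 mm from a nadir sum of about 25 mm or less

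*SAP*

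**What the plan says.** The closing paragraph of SAP 3.2.2.1 restates what counts as progression for PFS. It begins "Objective progression is defined as at least a 20% increase in the sum of the diameters of the target lesions", and the absolute part of the condition reads "target lesions (compared to previous minimum sum) and an absolute increase of >5 mm". Non-target progression or a new lesion also counts.

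The same threshold appears in four other places, each time inclusive:

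- Protocol Appendix F, Table F2: "At least a 20% increase in the sum of diameters of target lesions, taking as reference the smallest sum on study", and then "the sum must also demonstrate an absolute increase of at least 5mm".
- SAP 3.1.1.1, Table 4: "the sum must also demonstrate an absolute increase of at least 5 mm".
- SAP 3.1.1.1, rule for missing target-lesion data: ≥5 mm from nadir.
- SAP 3.1.1.1, scaling rule for lesions with intervention: ≥5 mm from nadir.

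SAP 3.1.1 states that the RECIST outcomes, PFS among them, are computed by program from the overall visit responses. Those come from Tables 4 to 6. SAP Section 6 names protocol version 7.0 as its basis and lists no departures, and the SAP amendment history does not mention this threshold.

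**The concern.** One event has two definitions in the current text. A growth of exactly 5 mm can be a progressive-disease visit response under Table 4 and yet fail the definition of objective progression in the PFS section.

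Exactly 5 mm is not an exotic value. On units, Protocol Appendix F says "All measurements should be recorded in millimetres". For a target lesion too small to measure, SAP 3.1.1.1 says "a value of 5mm will be entered into the database and used in TL calculations", while a lesion that has disappeared is recorded as 0 mm. A lesion that vanishes and is later faintly seen again therefore adds exactly 5 mm by convention.

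PFS and DoR are at stake, because SAP 3.2.2.3 ends the response on the date used for PFS. The stricter rule can postpone or remove an event but can never add one, so any error runs in one direction.

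**Working it through.** The plan gives no figure to reproduce here. The check compares the two rules case by case.

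**Inputs.**
- Rule A (Table F2, Table 4): increase over nadir ≥20% and ≥5 mm.
- Rule B (SAP 3.2.2.1): increase over nadir ≥20% and >5 mm.
- Rounding (SAP 3.1.1.1): "percentage changes from baseline and previous minimum should be rounded to one decimal place before assigning a TL response".
- Sums taken in whole millimetres. This is a simplification, since the documents fix the unit but not the precision.

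**Where they can differ.** The absolute conditions differ only at an increase of exactly 5 mm. There, rule A gives progression if 5 / nadir ≥ 20%, that is, nadir ≤ 5 / 0.20 = 25 mm. With the one-decimal rounding, 19.95% counts as 20.0%, so the limit becomes 5 / 0.1995 = 25.06 mm. For whole millimetres this changes nothing.

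**Enumeration.** Every nadir sum from 1 to 200 mm was paired with every increase from 0 to 100 mm. A nadir of 0 mm was left out because the percentage is then undefined. The rules disagree in exactly 25 pairs: +5 mm from each nadir of 1 to 25 mm. Examples:

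| Nadir (mm) | Follow-up (mm) | Increase | Rule A | Rule B |
|---|---|---|---|---|
| 10 | 15 | +5 mm, 50.0% | PD | not PD |
| 20 | 25 | +5 mm, 25.0% | PD | not PD |
| 25 | 30 | +5 mm, 20.0% | PD | not PD |
| 26 | 31 | +5 mm, 19.2% | not PD | not PD |
| 30 | 35 | +5 mm, 16.7% | not PD | not PD |
| 20 | 26 | +6 mm, 30.0% | PD | PD |

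A new lesion or non-target progression at the same visit gives progression under either text, so the difference also requires that neither is present.

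**What would follow if rule B were programmed.** There are two paths for an affected patient:

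1. Scanning continues, and the event moves to a later scan. One interval is 8 weeks up to Day 1277 and 10 weeks after it.
2. The investigator, working from Appendix F, calls progression at +5 mm. Protocol 5.1.1 has scans submitted only up to that point, so normally no later scan arrives. Under SAP 3.2.2.1 the patient is then censored at that same assessment, unless a death inside the missed-visit window supplies an event.

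In both paths the Kaplan-Meier curve is the same or higher than under rule A.

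**After correction.** With ≥5 mm in SAP 3.2.2.1, rules A and B are identical and the 25 conflicting pairs fall to 0.

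**The case against.** The strongest reply is that the SAP already settles which rule drives PFS. SAP 3.1.1 computes it from overall visit responses. SAP 3.2.2 opens with the same derivation. SAP 3.2.2.1 defines the event as RECIST 1.1 progression and, just before the disputed sentence, says that visit assessments feed into PFS. On that reading the strict sign is a slip in a closing summary. Most of this stands: it shows which text is wrong, and that the bias is conditional and not built into the analysis. It does not remove the conflict. The PFS section gives an explicit definition, no rule says which text prevails, and two programmers could code it differently.

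Some stronger readings are tempting but are not supported:

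- A reader might infer that every 5 mm growth is classified differently. Above a nadir of about 25 mm neither rule gives progression.
- A reader might set one 8-week interval (56 / 30.4375 = 1.84 months) against the assumed 19-month median and infer a shift of about 10%. That is the delay for one affected patient, not a change in the median, and the censoring path is the more likely one.
- A reader might try to simulate the share of progressions affected. The documents give no nadir distribution, growth rate or measurement error, so the answer would only reflect the chosen inputs. It would also have to allow for events from new lesions and non-target disease.
- A reader might expect DoR to disagree with PFS. It cannot, because both end on the same date.

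**Conclusion.** The contradiction is real and confined to one sentence of SAP 3.2.2.1. It matters only for a target-lesion increase of exactly 5 mm from a nadir sum of about 25 mm or less, with no other sign of progression, and only if that sentence, not the visit-response algorithm, is programmed. In that case PFS and DoR could only be lengthened. The size cannot be derived from the documents and is probably small.

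PFS and DoR are secondary Kaplan-Meier summaries in a single-arm study, with no hypothesis test attached. A reader might infer that the primary endpoint is also exposed. It is not: under SAP 2.1.1 a patient whom the investigator judges to have progressed stays evaluable even without programmatic progression. The point is worth correcting because the intended rule is clear and the remedy is trivial.

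**What to change.** In SAP 3.2.2.1, replace >5 mm with ≥5 mm. Alternatively, delete the sentence and refer to SAP Tables 4 to 6, so that the threshold is stated once and matches Protocol Table F2. Then confirm that the PFS program takes progression from the overall visit response and applies no separate strict threshold.

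The cost is one character or one sentence in the SAP and a short programming check. If the strict rule had already been coded, PFS and DoR may become very slightly shorter.
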